## **1. Protocol Synopsis**

**Title:** A Phase 1b Study Evaluating the Safety, Tolerability, Pharmacokinetics and Efficacy of Oprozomib in Combination With Pomalidomide and Dexamethasone in Subjects With Relapsed or Refractory Multiple Myeloma

**Study Phase:** 1b

**Indication:** Relapsed or Refractory Multiple Myeloma

**Hypothesis:**

At least one dose level of the formulations of oprozomib administered orally together with pomalidomide and dexamethasone is expected to achieve acceptable safety and tolerability in subjects with relapsed or refractory multiple myeloma.

**Primary Objective:**

- Identify the maximum tolerated dose (MTD) of oprozomib formulations in combination with pomalidomide and dexamethasone (OPomd) in subjects with relapsed or refractory multiple myeloma
- Evaluate the safety and tolerability of the OPomd combination in subjects with relapsed or refractory multiple myeloma

**Secondary Objective(s):**

- Characterize the pharmacokinetics (PK) of oprozomib
- Evaluate the efficacy of the OPomd combination according to International Myeloma Working Group (IMWG) uniform response criteria
- Identify the recommended formulation and Phase 3 dose (RP3D) of oprozomib in combination with pomalidomide and dexamethasone in subjects with relapsed or refractory multiple myeloma

**Primary Endpoint:**

- Determine the MTD for each formulation of oprozomib in combination with pomalidomide and dexamethasone as the dose that has the highest posterior probability of having a dose limiting toxicity (DLT) rate within the target toxicity interval (15% to 25%), while the posterior probability of excessive/unacceptable toxicity (> 25% to 100%) is < 40%
- Incidence of treatment-related, treatment-emergent adverse events and changes in laboratory test results

**Secondary Endpoints:**

- PK parameters of oprozomib including, but not limited to, maximum observed concentration ( $C_{max}$ ), time to  $C_{max}$  ( $t_{max}$ ), and the area under the concentration-time curve from time 0 to the time of the last quantifiable concentration ( $AUC_{last}$ )
- Overall response and best overall response according to the IMWG uniform response criteria, progression free survival (PFS), and duration of response (DOR)

### Study Design:

This is a Phase 1b, multicenter, non-randomized, open-label, dose-exploration study of up to two formulations of oprozomib (an “immediate release” formulation [IR], and an “extended release gastro-retentive” formulation [GR]) administered according to a 2/7 schedule (two consecutive days per week), in combination with pomalidomide and dexamethasone in subjects with relapsed or refractory multiple myeloma. The evaluation of the different formulations will start with the IR (for the initial 1 to 2 dose levels) however, for most of the study the two oprozomib formulations will be tested in parallel.

The study will be conducted in two sequential parts:

- Part 1 – Evaluation of 2 formulations of oprozomib administered at 150 mg/day dose level in combination with dexamethasone (Od) only
- Part 2 – Evaluation of 2 formulations of oprozomib administered at increasing dose levels (dose escalation) in combination with pomalidomide and dexamethasone (OPomd)

Part 1 will test each formulation of oprozomib in combination with dexamethasone to evaluate the safety and tolerability of oprozomib in combination with dexamethasone at the starting dose level. Testing will begin with the IR formulation. If a dose modification of oprozomib is necessary, this will be decided based on analysis of emerging safety and PK data. Part 2 dose escalation will use the Bayesian 2-parameter logistic regression model with the new continual reassessment method (NCRM) applied to observed DLTs (Neuenschwander, 2008). Testing will begin with the IR formulation of oprozomib, and the starting dose level will be chosen based on the oprozomib dose determined during Part 1. All subjects will be treated during the first week only with a fixed, initial dose level of oprozomib. For all dosing days thereafter, the subjects will be treated with the appropriate dose level of oprozomib according to the dose escalation cohort being evaluated. It is anticipated that in Part 2, seven dose levels of oprozomib IR (between 150 mg and 300 mg/day, in increments of 25 mg) will be tested in combination with pomalidomide and dexamethasone. The number of dose levels, the increment of change as well as the minimum and maximum dose level of oprozomib to be tested may be adjusted during the study based on emerging safety and PK data. The application of the Bayesian algorithm will stop when the DLT rate of the recommended MTD has a probability within the target toxicity interval (15% to 25%) of  $\geq 40\%$ , an excessive/unacceptable interval ( $>25\%$  to 100%) of  $< 40\%$ , and a minimum of 6 subjects have been treated at the MTD level or when the sample size reaches 36 subjects. In the event that evaluation of additional subjects is deemed necessary by the dose level review team (DLRT), extra subjects may be enrolled. The testing of the GR formulation will start after the first one or two cohorts of IR have been evaluated. The starting dose for the GR formulation will be determined based on the safety and PK data observed in the first cohorts of the IR dose escalation, and it will be at least one dose level lower than the highest dose tested of the IR formulation. Once the MTDs are determined, the DLRT will review the available safety, efficacy, PK, and [REDACTED] data and recommend a formulation and a dose level for administration of oprozomib in the OPomd combination in future studies.

For additional details please refer to Section 6.1 and the Study Schema.

**Sample Size:** Approximately 64 DLT-evaluable subjects will be enrolled in this phase 1b study. In Part 1, at least 3 DLT-evaluable subjects will be enrolled for each of the oprozomib formulations. In Part 2, a Bayesian design will be applied to evaluate the oprozomib formulations (IR and GR) administered at increasing dose levels in combination with pomalidomide and dexamethasone. The maximum sample size for testing the IR formulation is set to 36 DLT-evaluable subjects. The anticipated sample size under the assumption of 11 cohorts evaluated for the GR formulation is 22 DLT-evaluable subjects.

#### **Summary of Subject Eligibility Criteria:**

Subjects  $\geq$  18 years of age with pathologically documented, definitively diagnosed, multiple myeloma disease relapsed or refractory after at least 2 prior lines of therapy. Prior therapeutic treatment or regimens must include lenalidomide and a proteasome inhibitor. Once consented to the study, subjects will undergo safety tests and provide a medical history to confirm they meet all requirements of the study.

For a full list of eligibility criteria, please refer to Section 7.1 and Section 7.2.

#### **Investigational Product**

##### **Amgen Investigational Product Dosage and Administration:**

Oprozomib will be administered orally according to a 2/7 schedule on days 1, 2, 8, 9, 15, 16, 22 and 23 of each 4 week cycle. Lansoprazole or another oral proton-pump inhibitor (PPI) is required (H2 antagonists are recommended if subject has intolerance or hypersensitivity to PPI) for the duration of treatment to prevent gastrointestinal (GI) toxicities. Oral hydration of 1.5 to 2 liters per 24 hours must be instituted in all subjects 24 hours prior to initiation of therapy for every cycle and continued throughout every day of oprozomib dosing.

The IR formulation of oprozomib will be supplied in two tablet strengths of 25 mg and 50 mg in bottles of 30 tablets stored at 5°C with desiccant, and it is recommended to be taken after a low fat meal. The GR formulation of oprozomib will be supplied in two tablet strengths of 25 mg and 100 mg in bottles of 30 tablets stored at 5°C with desiccant and is required to be taken immediately after a main meal that contains the highest calorie and fat content.

During Part 1, the initially tested dose level of oprozomib in combination with dexamethasone only, will be 150 mg/day for both formulations.

During Part 2, all subjects will be treated during the first week only, with a fixed, initial daily dose of oprozomib (currently 150 mg/day, but may be adjusted during the study based on emerging data), and for all dosing days thereafter with the appropriate dose level of oprozomib according to the dose escalation cohort evaluated. For the IR formulation, the currently anticipated dose levels to be tested are 150, 175, 200, 225, 250, 275 and 300 mg/day. The decision for the dose levels to be tested with the GR formulation will be based on information obtained from the Part 2 IR cohorts.

#### **Non-investigational Product**

##### **Non-Amgen Non-investigational Product Dosage and Administration:**

Dexamethasone is available as tablets containing 4 or 6 mg of dexamethasone drug substance for oral administration. All subjects will receive 20 mg of dexamethasone on each oprozomib dosing day. It is recommended that dexamethasone be taken with food or after meals.

Additional product information is provided in the Dexamethasone Prescribing Information (Pfizer Laboratories, 2012).

Pomalidomide is available as a capsule containing 1, 2, 3, and 4 mg of pomalidomide drug substance for oral administration. Pomalidomide will be administered at a dose of 4 mg on days 1 to 21 of repeated 28-day cycles. In Part 1, pomalidomide may be added to the Od treatment regimen once the initial cohort in Part 2 establishes a first dose level of oprozomib as safe and tolerable in combination with pomalidomide and dexamethasone. In Part 2, all subjects will receive pomalidomide starting on day 1 of cycle 1. Pomalidomide may be taken with water. Inform subjects not to break, chew, or open the capsules. Pomalidomide may be taken with or without food. Anticoagulant or antiplatelet medication is recommended as prophylaxis for venous and arterial thromboembolism based on assessment of the subject's underlying risk factors. Additional product information is provided in the Pomalidomide Prescribing Information (**Pomalidomide U.S. Prescribing Information for United States; for other countries, see appropriate prescribing information**).

**Procedures:** After written informed consent has been obtained, all screening tests and procedures will be performed within 28 days of administration of the first dose of oprozomib (day 1), unless otherwise noted. Subjects will be seen in clinic where evaluations will be performed including physical examination, vital signs, clinical laboratory tests, ECGs, PK, and [REDACTED] sample collections. For a full list of study procedures, including the timing of each procedure and the Schedule of Assessments, please refer to Section 10.

#### **Statistical Considerations:**

The DLRT will hold dose level review meetings (DLRMs) to review data, monitor safety and make decisions on dose escalation/change.

#### **Primary Analysis**

The objectives of the primary analysis are to determine the MTD for each formulation of oprozomib in combination with pomalidomide and dexamethasone and further evaluate the safety and tolerability of the OPomd combination in subjects with relapsed or refractory multiple myeloma. In addition, this analysis will be used, as possible, to recommend the most appropriate oprozomib dose and formulation to be tested in future clinical trials in an OPomd combination, based on safety, tolerability, efficacy, PK and other available data from all the escalation cohorts.

The primary analysis will be based on subject data collected up to two months from the date of last subject enrollment. A Bayesian 2-parameter logistic regression model, the NCRM will be applied to observed DLTs to find MTDs for the oprozomib formulations (Neuenschwander, 2008). The prior distribution and the data available after each dose cohort are applied to the algorithm that computes the posterior distribution of the DLT rate at each dose level. The posterior probabilities of the estimated DLT rate at each dose to fall into target toxicity interval (15% to 25%) or excessive/unacceptable toxicity interval (> 25% to 100%) will be used in the dose escalation decision and the final determination of the MTD. Refer to study design section for a detailed description of the dose escalation method. The safety analyses will be based on the safety evaluable population, which is defined as all subjects who received any amount of the study treatment regimen oprozomib, dexamethasone and pomalidomide. Safety and tolerability will be assessed through summaries of study drug administration, DLTs, adverse events, changes in selected laboratory analytes, and vital signs by dose level.

The primary efficacy analysis will be performed in all subjects that received at least one cycle of OPomd and have baseline disease assessment and at least one post-baseline disease assessment. Both overall response rate and the best overall response will be summarized.

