#### **5.5.5 Clinical Experience – Phase 1**

**As of the 21 August 2020 data cutoff date, Study 20160104 had enrolled 54 subjects with RRMM: 36 with the IR formulation and 18 with the GR formulation. Forty-five enrolled subjects were evaluable for efficacy, with 9 subjects in combination with dexamethasone and 23 subjects with pomalidomide and dexamethasone. Preliminary results demonstrated anti-tumor activity in RRMM, with 20 of 28 evaluable subjects having a PR or better with the IR formulation and 3 of 8 having a PR or better with GR formulation in combination with pomalidomide and dexamethasone.**

**A total of 6 DLTs were observed. For the GR formulation, 1 subject with the 150 mg GR formulation in the Opomd group experienced grade 4 neutropenia and subsequently developed febrile neutropenia (reported as separate DLT events). The DLRM recommended to escalate to 200 mg; one DLT was observed (grade 4 thrombocytopenia). For the IR formulation, 1 DLT was observed with the 150 mg dose and the 200 mg dose, and 2 DLTs were observed with the 250 mg dose across both the ODex and OPomd groups. A summary of DLTs is provided in Table 1.**

**Table 1. Subject Incidence of Dose-limiting Toxicities (DLT) During DLT Evaluation Period by Preferred Term in Descending Order of Frequency (DLT-Evaluable Analysis Set)**

Preferred Term	Non-roll Over Subjects											
	ODex 2/7 Schedule			OPomd 2/7 Schedule								
	IR 150 mg/day (N = 5)	GR 150 mg/day (N = 8)	ODex 2/7 Total (N = 13)	IR 150 mg/day (N = 4)	GR 150 mg/day (N = 4)	IR 200 mg/day (N = 8)	GR 200 mg/day (N = 5)	IR 225 mg/day (N = 10)	IR 250 mg/day (N = 8)	OPomd 2/7 Total (N = 39)	Total Subjects (N = 52)	
Number of subjects reporting DLTs	0 (0.0)	0 (0.0)	0 (0.0)	1 (25.0)	1 (25.0)	1 (12.5)	1 (20.0)	0 (0.0)	2 (25.0)	6 (15.4)	6 (11.5)	
Lipase increased	0 (0.0)	0 (0.0)	0 (0.0)	1 (25.0)	0 (0.0)	0 (0.0)	0 (0.0)	0 (0.0)	1 (12.5)	2 (5.1)	2 (3.8)	
Abdominal pain	0 (0.0)	0 (0.0)	0 (0.0)	0 (0.0)	0 (0.0)	0 (0.0)	0 (0.0)	0 (0.0)	1 (12.5)	1 (2.6)	1 (1.9)	
Acute kidney injury	0 (0.0)	0 (0.0)	0 (0.0)	0 (0.0)	0 (0.0)	1 (12.5)	0 (0.0)	0 (0.0)	0 (0.0)	1 (2.6)	1 (1.9)	
Febrile neutropenia	0 (0.0)	0 (0.0)	0 (0.0)	0 (0.0)	1 (25.0)	0 (0.0)	0 (0.0)	0 (0.0)	0 (0.0)	1 (2.6)	1 (1.9)	
Neutrophil count decreased	0 (0.0)	0 (0.0)	0 (0.0)	0 (0.0)	1 (25.0)	0 (0.0)	0 (0.0)	0 (0.0)	0 (0.0)	1 (2.6)	1 (1.9)	
Thrombocytopenia	0 (0.0)	0 (0.0)	0 (0.0)	0 (0.0)	0 (0.0)	0 (0.0)	1 (20.0)	0 (0.0)	0 (0.0)	1 (2.6)	1 (1.9)	

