##### **Part 2**

The dose escalation design will use the Bayesian 2-parameter logistic regression model, the NCRM applied to observed DLTs (Neuenschwander, 2008).

For the IR formulation, the starting dose level is 150 mg/day (2/7 schedule); the maximum and the minimum planned dose levels are 300 mg/day and 150 mg/day, respectively. Dose levels and escalation and de-escalation increments may be adjusted based on data generated in the study. One or more cohorts of at least 2 subjects may be enrolled at each dose level, depending on the toxicity observed. In accord with NCRM, the relationship between dose and the probability of DLT will be updated as additional subject safety information becomes available. After all subjects enrolled at the starting dose level are DLT-evaluable, the Bayesian Logistic Regression (BLR) model will be updated, and the NCRM will recommend the next dose level from the updated probabilities for target toxicity interval and excessive/unacceptable toxicity interval. The next cohort (eg. the Dose Level 2 or continuation of Dose Level 1) will be the dose with the highest posterior probability of having a toxicity rate in the target toxicity interval, which is defined as 15% to 25%, and will be subject to the constraint that the probability of excessive/unacceptable toxicity, which is defined as > 25% to 100%, is less than 40%. The DLRT will review the safety data and dose level recommended by the algorithm after every cohort has completed the DLT period. The DLRT will decide to expand the cohort at the current dose level, advance to the next dose level, or de-escalate to a lower dose level, based on the available data. Dose level skipping will be allowed in dose escalation decisions with a maximum increment of 50 mg/day. The NCRM will continue to assign subjects to subsequent dose levels based on the cumulative DLT data, until either the DLT rate of the recommended MTD has a probability of within the target toxicity interval (15%-25%)  $\geq$  40%, an excessive/unacceptable interval ( $>25\%-100\%$ )  $<$  40%, and a minimum of 6 subjects have been treated at the candidate MTD or the predetermined maximum sample size of 36 DLT-evaluable subjects is reached, whichever comes first.

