4.2 Subgroups

5. Definitions

Age at Enrollment

Subject age at enrollment will be determined using the age in years reported in the clinical database.

Baseline

For any variable, unless otherwise specified the baseline is the last assessment taken prior to the first administration of study treatment. For parameters/assessments not scheduled to be performed (or scheduled but not performed) on the same day as the

first administration of study treatment, the baseline value is the value from the screening period measured closest to the day of first administration of study treatment.

Baseline and Post-Baseline ECG Values in Triplicate

The baseline ECG is defined as the mean of all pre-dose assessments; the mean of values in a triplicate should be calculated before taking the mean of the triplicate averages.

For all post-baseline ECG, the mean value for measurements taken at the same assessment will be calculated and used in the analysis.

For pre and post dose ECG measurements, unscheduled ECG measurements taken up to 5 minutes after the last assessments of a triplicate will be included in the average for a timepoint. Where an ECG is missing within a triplicate, all available data will be averaged for that timepoint.

Bazett-corrected QT Interval (QTcB)

The Bazett correction will be calculated from the investigator reported QT (msec) and RR interval (msec), as follows: $QTcB=QT/(RR/1000)^{1/2}$

Change From Baseline

Change from Baseline is the arithmetic difference between post-dose assessments and Baseline value.

Change (absolute) from Baseline=(Post-baseline Value – Baseline Value)

Change (percent) from Baseline=[(Post-baseline Value – Baseline Value)/Baseline Value]x100

Dose Limiting Toxicities (DLT) Window

The DLT window will be the initial 28 days of study treatment. The DLT window may be extended to assess events starting within the window in case the DLT definition is time dependent. Any adverse event occurring outside the DLT window that is determined by the investigator to be possibly related to the investigational product, which is seen more frequently or is more severe than expected or is persistent despite appropriate management, can be determined to be a DLT upon unanimous decision by the DLRT after review of the adverse event and all available safety data.

DLT Evaluable

In order to be DLT-evaluable, a subject would receive the doses of study treatment as specified below during the 28 day DLT window:

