7.2 Primary Analysis

Non-roll over subjects:

The main objectives of the primary analysis are to determine the MTD for each formulation of oprozomib in combination with pomalidomide and dexamethasone and further evaluate the safety, tolerability and efficacy of the OPomd combination in subjects with relapsed or refractory multiple myeloma. In addition, this analysis will be used to possibly recommend the most appropriate oprozomib dose and formulation to be tested in future clinical trials in an OPomd combination. The selection of the oprozomib

recommended dose and formulation will be based on all data from the escalation cohorts.

Safety and tolerability will be assessed through summaries of study drug administration, DLTs, adverse events, changes in selected laboratory analytes, vital signs, and physical findings by dose level. Means and standard deviations will be used to summarize the total dose for each component of study drug received. All summaries will be presented by the assigned dose level and for all subjects.

All adverse event data will be listed by study site, dose level, subject identification number, and study day. All adverse events will be summarized by preferred term, appropriate thesaurus levels, and CTCAE (Version 4.03) toxicity grade. In addition, all serious adverse events, including deaths, will be listed separately and summarized.

Efficacy analyses of ORR and BOR will be performed using both the efficacy and safety population as defined previously.

Roll-over subjects: the main objective of the primary analysis of roll-over subjects is to evaluate the safety profile for all subjects on continued oprozomib treatment. Safety profile will be presented through descriptive statistics of safety data (treatment-emergent serious adverse events, treatment-emergent adverse events).

The primary analysis will be based on subject data collected up to two months from the date of last subject enrollment. **All available data up to and including the data cutoff date will be cleaned and a locked database will be used in the analysis.**

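### The Part 2 stopping rule counts its minimum of 6 as treated subjects but its cap of 36 as DLT-evaluable subjects, and no DLT-evaluable analysis set is defined

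*Protocol*

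**What the plan says.** **Stopping rule.** Protocol 9.2.1.2 (Part 2) requires a posterior probability of at least 40% for the 15-25% DLT interval, a probability below 40% for rates above 25%, and a head count: "a minimum of 6 subjects have been treated at the candidate MTD or the predetermined maximum sample size of 36 DLT-evaluable subjects is reached". The synopsis (Study Design) words the count as "a minimum of 6 subjects have been treated at the MTD level or when the sample size reaches 36 subjects", and SAP 3.1 repeats it. Elsewhere the same 36 is called DLT-evaluable (synopsis Sample Size, Protocol 6.3 and 13.2, SAP 3.2).

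**Evaluability.** SAP 5 defines a subject's status: "In order to be DLT-evaluable, a subject would receive the doses of study treatment as specified below during the 28 day DLT window". It needs all planned oprozomib doses, 17 of 21 pomalidomide doses and 6 of 8 dexamethasone doses. The dose level review team (DLRT) rules on subjects who stop or miss oprozomib for reasons other than a DLT. Protocol 6.4 has the same criteria and says that non-evaluable subjects are replaced.

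**Analysis sets.** Protocol 13.1.2 and SAP 6 list safety, efficacy and PK sets only. The synopsis says "The safety analyses will be based on the safety evaluable population, which is defined as all subjects who received any amount" of study treatment, and its next sentence begins "Safety and tolerability will be assessed through summaries of study drug administration, DLTs, adverse events". Protocol 13.4.2.1 and SAP 9.6.2 plan DLT counts by dose and formulation and name no set. The model is said only to be applied to observed DLTs. The one DLT table in the documents, Table 1 in Protocol 5.5.5, is titled "DLT-Evaluable Analysis Set".

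**The concern.** The minimum of 6 is there so that an MTD is not declared on too few subjects who completed the DLT assessment. A subject replaced for incomplete exposure adds little or nothing to the DLT estimate. With 4 evaluable and 2 replaced subjects at a dose, 4 + 2 = 6 have been treated. The count is then met with 4 informative subjects, while the cap in the same sentence would count only those 4.

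The missing analysis set is a related gap. The MTD is a primary endpoint, yet no section says which subjects enter the model or form the denominator of the DLT tables. Both choices would be left to the programmer.

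**Working it through.** **1. The plan's own figures.** Part 1 gives 3 + 3, IR 36, and GR 11 cohorts × 2 = 22. The total is 3 + 3 + 36 + 22 = 64, and Part 2 is 36 + 22 = 58. Both match the stated DLT-evaluable totals, so the sample size is built in evaluable subjects. Only the 6 is stated in treated subjects.

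**2. Why fewer than 6 matters.** For a true DLT rate of 30% (assumed, above the target), P(0 or 1 DLT) = 0.7^n + n × 0.3 × 0.7^(n−1).

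| Evaluable n | P(0 or 1 DLT) |
|---|---|
| 6 | 0.118 + 0.303 = 42% |
| 5 | 0.168 + 0.360 = 53% |
| 4 | 0.240 + 0.412 = 65% |
| 3 | 0.343 + 0.441 = 78% |

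**3. Does the 6 ever bind?** It is one of three joint conditions. If each dose stood alone with a flat Beta(1,1) prior, the highest attainable probability of the 15-25% interval would be 27% with 6 subjects (1 DLT), 36% with 12 (2 DLTs) and 43.5% with 20 (4 DLTs). The 40% threshold would then bind long before the count.

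The planned two-parameter model borrows across doses. Assume logit p(d) = α + β log(d/225), with α centred at logit 0.20 (SD 1) and log β centred at 0 (SD 0.5). Take 1/6, 1/6, 1/6 and 1/4 DLTs at 150, 175, 200 and 225 mg. At 225 mg the target probability is about 46-47% and the probability of a rate above 25% is about 31%, so both thresholds pass with 4 evaluable subjects. The same data give about 48% and 22% at 200 mg, which would therefore be the recommended dose. This example shows only that borrowing can carry a dose with 4 subjects past the thresholds. It is not itself a premature stop.

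**4. How often.** The design was simulated with the seven IR doses, cohorts of 2, a maximum step of 50 mg, at most 36 evaluable subjects and the plan's thresholds. Assumed inputs were three toxicity curves, 10-20% non-evaluable, and the model in step 3 under two priors. Several sets of 300 to 800 runs per setting gave these ranges:

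| Assumed prior (SD of α, SD of log β) | Precision stops with <6 evaluable at the selected dose: 6 counted as treated | 6 counted as evaluable | Mean extra subjects |
|---|---|---|---|
| Vague (2, 1) | about 0.4-11% | 0% | below 1 |
| Tighter (1, 0.5) | about 6-32% | 0% | up to about 2 |

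Under the vague prior, one set of runs put such stops at 1-4% of all trials. The chance of selecting an in-target or an over-toxic dose differed between the two counts by less than 1 percentage point under the vague prior. Under the tighter prior it differed by up to about 4 points, and for over-toxic doses in no consistent direction.

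**5. The DLT denominator.** Table 1's cohort Ns are 5 + 8 = 13 (ODex) and 4 + 4 + 8 + 5 + 10 + 8 = 39 (OPomd), in total 52. Its rates reproduce: 6/39 = 15.4% and 6/52 = 11.5%. Table 2, on the safety set, has the same N in all eight cohorts. Either no treated subject was non-evaluable or the evaluability filter removed nobody, and the tables cannot show which. Section 5.5.5 also reports 54 enrolled against 52 in both sets, although Protocol 8 makes the first dose part of enrollment. That difference should be reconciled.

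**The case against.** The strongest reply is that this is loose wording with no demonstrated harm. Much of that stands.

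- The 36 is called DLT-evaluable in enough places that its meaning is not in doubt. Only the unit of the 6 is open.
- The 6 cannot stop the algorithm alone, and the DLRT may enroll extra subjects. With little borrowing across doses the posterior condition binds first.
- The frequencies in step 4 rest on an assumed prior, assumed curves and an assumed non-evaluable share.

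A reader might also infer three stronger things that the documents do not support.

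- *That DLTs are formally assigned to the safety population.* This rests on two adjacent synopsis sentences. The statement in Protocol 13.3.2 and SAP 7.2 that "All summaries will be presented by the assigned dose level and for all subjects" reads naturally as dose columns plus a pooled total, which is Table 1's layout.
- *That an all-treated denominator always lowers the DLT rate.* Protocol 9.2.1.4 lets the DLRT declare DLTs outside the window, so a non-evaluable subject can carry one. With 2 DLTs in 6 evaluable subjects and 2 replaced, the rate falls from 33.3% to 2/8 = 25.0% if neither replaced subject has a DLT. It rises to 3/8 = 37.5% if one does.
- *That a crude rate crossing 15% or 25% changes the MTD.* The interval applies to the model posterior. Crude dilution leaves that unchanged if the model uses evaluable subjects, which the design implies but never states.

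The mixed unit within one stopping sentence and the absence of a defined set remain.

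**Conclusion.** The concern holds as a defect in a stated decision rule. Followed literally, the rule lets replaced subjects complete the minimum of 6, so the algorithm can stop with fewer than 6 informative subjects at the MTD. Under the assumptions in step 4 this affects roughly 0.4-11% of precision stops with a vague prior and 6-32% with a tighter one. The end points are approximate because the prior and the non-evaluable share are not in the documents. No consistent change in the selected dose was found.

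The missing DLT-evaluable set is a gap in specification. Dilution of reported DLT rates is neither shown nor excluded by Tables 1 and 2. The point is worth correcting because it concerns a primary endpoint and costs little, but it is not evidence that an MTD was or would be wrong.

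**What to change.** - In Protocol 9.2.1.2, the synopsis and SAP 3.1, state both the 6 and the 36 as DLT-evaluable subjects.
- Add a DLT-evaluable analysis set to Protocol 13.1.2 and SAP 6, carrying over the criteria and the DLRT's role from Protocol 6.4 and SAP 5.
- Name that set as the model input, and as the denominator for DLT incidence in the synopsis, Protocol 13.3.2 and 13.4.2.1, and SAP 7.2 and 9.6.2.
- Report the number of treated but non-evaluable subjects per dose and formulation, and list any DLTs in them.

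The cost is wording in two documents, plus on average about 0-2 extra subjects before a precision stop, depending on the prior. No dose level, DLT definition or treatment rule changes.
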